8.3 Exclusion criteria

Subjects must not enter the trial if any of the following exclusion criteria are fulfilled:

1. Concurrent skin diseases on the hands, e.g. tinea manuum.
2. Active atopic dermatitis in regions other than the hands or psoriasis requiring medical treatment.
3. Clinically significant infection (e.g., impetiginised hand eczema) on the hands.
4. Systemic treatment with immunosuppressive drugs (e.g., methotrexate, cyclosporine, azathioprine), immunomodulating drugs (e.g., janus kinase inhibitors), retinoids (e.g., alitretinoin), or corticosteroids within 4 weeks prior to baseline (inhaled or intranasal steroids corresponding to up to 1 mg prednisolone for asthma or rhinitis may be used).
5. Psoralen ultraviolet A (PUVA) or ultraviolet B (UVB) therapy on the hands within 4 weeks prior to baseline.
6. Receipt of live attenuated vaccines 4 weeks prior to baseline.
7. Cutaneously applied treatment with immunomodulators (e.g., phosphodiesterase-4 (PDE-4) inhibitors, pimecrolimus, tacrolimus) or topical corticosteroids on the hands within 2 weeks prior to baseline.
8. Use of systemic antibiotics or cutaneously applied antibiotics on the hands within 2 weeks prior to baseline.
9. Change in systemic antihistamine therapy within 2 weeks prior to baseline i.e., subjects must not start antihistamine treatment or change the current dosage regime within 2 weeks prior to baseline.
10. Other cutaneously applied therapy on the hands (except for the use of subject's own emollients) within 1 week prior to baseline.

11. Cutaneously applied treatments in regions other than the hands, which could interfere with clinical trial evaluations or pose a safety concern within 1 week prior to baseline.
12. Treatment with any marketed biological therapy or investigational biologic agents (including immunoglobulin, anti-IgE, and dupilumab):
 - Any cell-depleting agents including but not limited to rituximab: within 6 months prior to baseline, or until lymphocyte count returns to normal, whichever is longer.
 - Other biologics: within 3 months or 5 half-lives, whichever is longer, prior to baseline.
13. Treatment with any non-marketed drug substance (that is, an agent which has not yet been made available for clinical use following registration) within the last 4 weeks prior to baseline or 5 half-lives whichever is the longest.
14. Clinically significant infection within 4 weeks prior to baseline which, in the opinion of the investigator, may compromise the safety of the subject in the trial, interfere with evaluation of the IMP, or reduce the subject's ability to participate in the trial.
Clinically significant infections are defined as:
 - A systemic infection.
 - A serious skin infection requiring parenteral (intravenous or intramuscular) antibiotics, antiviral, or antifungal medication.
15. Tuberculosis requiring treatment within 12 months prior to screening and/or subjects with a positive blood test for tuberculosis at screening*.
* Subjects with high risk of latent tuberculosis (e.g. prior residence in or travel to countries with high prevalence of tuberculosis, close contact with a person with active tuberculosis, or a history of active or latent tuberculosis where an adequate course of treatment cannot be confirmed) must be tested.
16. History of any known primary immunodeficiency disorder including a positive human immunodeficiency virus (HIV) test at screening, or the subject taking antiretroviral medications as determined by medical history and/or subject's verbal report.
17. Major surgery within 8 weeks prior to screening, or planned in-patient surgery or hospitalisation during the trial period.

18. History of cancer:

- Subjects who have had basal cell carcinoma, localised squamous cell carcinoma of the skin or in situ carcinoma of the cervix are eligible provided that the subject is in remission and curative therapy was completed at least 12 months prior to screening.
- Subjects who have had other malignancies are eligible provided that the subject is in remission and curative therapy was completed at least 5 years prior to screening.

19. Any disorder, including but not limited to cardiovascular, gastrointestinal, hepatic, renal, neurological, musculoskeletal, infections, endocrine, metabolic, haematological, immunological, psychiatric, or major physical impairment, which is not stable in the opinion of the investigator and could:

- Affect the safety of the subject throughout the trial.
- Influence the findings of the trial or their interpretations.
- Impede the subject's ability to complete the entire duration of the trial.

20. Any abnormal finding which may:

- Put the subject at risk because of their participation in the trial.
- Influence the results of the trial.
- Influence the subject's ability to complete the trial.

The abnormal finding must be clinically significant and observed during the screening period. Examples include abnormal findings in physical examination, vital signs, ECG, haematology, clinical chemistry, or urinalysis.

21. Positive hepatitis B surface antigen (HBsAg), hepatitis B surface antibody (HBsAb), hepatitis B core antibody (HBcAb), or hepatitis C virus antibody (anti-HCV) serology at screening. Subjects with positive HBsAb may be randomised provided they are hepatitis B vaccinated and have negative HBsAg and HBcAb.

22. Alanine aminotransferase or aspartate aminotransferase level ≥ 2.0 times the upper limit of normal range (ULN) at screening.

23. Known or suspected hypersensitivity to any component(s) of the IMP.

24. Current participation in any other interventional clinical trial.

25. Previously randomised in this clinical trial.

26. Previously participated in a clinical trial with delgocitinib (LEO 124249).
27. History of chronic alcohol or drug abuse within 12 months prior to screening, or any condition associated with poor compliance as judged by the investigator.
28. Employed at the trial site or directly involved with the planning or conduct of the trial, or immediate family members of such individuals.
29. Legally institutionalised.
30. Pregnant or lactating.

8.4 Screening and screening failures

Trial participation begins once written informed consent is obtained. Refer to [Appendix 3B](#) for details on the informed consent process. Once informed consent is obtained, a subject identification number (subject ID) will be assigned by a central interactive response technology (IRT) system and the screening evaluations to assess eligibility may begin. The subject ID will be used to identify the subject during the screening process and throughout trial participation, if applicable. Subjects, who have given written informed consent to participate in the trial and who have been assigned a subject ID are considered 'screened' subjects.

The investigator will maintain a log of all consented subjects at the trial site (subject identification list). This log will include each subject's identity, date of consent and corresponding subject ID so that any subject may be identified if required for any reason. The log must not be copied or retained by LEO. In addition, the investigator will maintain a log of all subjects considered for screening, whether they have provided written informed consent or not (screening log). This log will be anonymous and will include the reason(s) for not entering the trial, if applicable, or the allocated subject ID.

Screening failures

Screening failures are defined as subjects who consent to participate in the trial but are not subsequently randomly assigned to trial treatment. A minimal set of information is required to ensure transparent reporting of screening failure subjects to meet the Consolidated Standards of Reporting Trials (CONSORT) publishing requirements ([12](#)) and to respond to queries from regulatory authorities. Individuals who do not meet the criteria for participation in the trial (screening failures) may not be re-screened. However, if the reason for screening failure is administrative e.g., delayed test results and not due to the subject failing to meet the eligibility criteria, re-screening may be permitted. Individuals who are re-screened will get a new subject ID. The following data will be collected in the eCRF for screening failures:

- Date of informed consent.
- Demographics (date of birth, age, sex, ethnicity, race).
- Reason for screening failure:
 - Failure to meet eligibility criteria (specify which).
 - Withdrawal by subject.
 - Capping limitation in IGA baseline severity.
 - Other (specification is required).
- Date of screening failure.
- Any AEs and serious AEs (SAEs).

In case of any SAEs, these must be followed-up as described in Section 13.7.

9 Treatments

9.1 Trial product description

Delgocitinib is a pan-JAK inhibitor, which is presented in this trial in a cream formulation for cutaneous application. Refer to [Panel 4](#) for further details.

Panel 4: Identification of IMPs

Investigational medicinal product	Formulation	Active ingredient and formulation strength	Pack size	Source
Delgocitinib cream 1 mg/g	Cream	Delgocitinib 1 mg/g	15 g	CCI [REDACTED]
Delgocitinib cream 3 mg/g	Cream	Delgocitinib 3 mg/g	15 g	CCI [REDACTED]
Delgocitinib cream 8 mg/g	Cream	Delgocitinib 8 mg/g	15 g	CCI [REDACTED]
Delgocitinib cream 20 mg/g	Cream	Delgocitinib 20 mg/g	15 g	CCI [REDACTED]
Delgocitinib cream vehicle	Cream	Vehicle	15 g	CCI [REDACTED]

9.2 Administration of IMP

The IMP (delgocitinib cream 1, 3, 8, or 20 mg/g or delgocitinib cream vehicle) will be administered as a twice daily cutaneous application for 16 weeks. The applications will be performed approximately 12 hours apart. Instructions for use will be provided.

A thin layer of delgocitinib cream covering the affected areas on the hands will be applied. The maximum use depends on the size of the affected area and the size of the hands. One tube of 15 g delgocitinib cream is considered maximum for treatment of the whole surface of both hands twice daily for 1 week.

The first application of the IMP will occur at the trial site. Prior to the first IMP application, the subject will be instructed how much cream to be applied and which area(s) to be treated. Only the affected area(s) on the hand(s) will be treated. If new lesions occur on initially untreated area(s) of the hand(s), these new lesions will be treated with IMP as well. The subjects will be advised to contact the investigator before initiating treatment of new lesions. The IMP application on initially affected areas and new lesions will continue until Week 16.

regardless of clearance status. The last IMP application will occur at the subject's home before the subject attends the visit scheduled at Week 16.

The IMP will be dispensed by the investigational staff at the visits scheduled in Section 4. The IRT will assign the required kit number(s) for each subject at each dispensing visit.

The investigator will use clinical judgement to treat any symptoms connected with an overdose.

9.3 Treatment assignment

Subjects who have been found to meet all the inclusion criteria and not to fulfil any of the exclusion criteria will be randomised at baseline (Day 1) to receive treatment with either delgocitinib cream (1, 3, 8, or 20 mg/g) or delgocitinib cream vehicle. The treatment assignment occurs on the basis of a computer-generated randomisation scheme in a 1:1:1:1:1 ratio.

Subjects eligible on selection criteria at baseline may be prevented from being randomised into the trial due to the applied capping limitation in IGA baseline severity and regional enrolment (as described in Section 7.2). Due to this capping, the sponsor will actively monitor the subjects in the screening period to minimise the number of subjects that may be excluded from the trial prior to randomisation.

The IRT will be used to control randomisation and stratification factors, along with IMP supply chain and expiry tracking.

9.3.1 Blinding

The packaging and labelling of the IMPs will contain no evidence of their identity. It will not be possible to differentiate between the IMPs solely by sensory evaluation.

9.3.2 Emergency unblinding of individual subject treatment

While the safety of a subject always comes first, it is still important to carefully consider if unblinding is necessary to ensure a subject's safety. An emergency unblinding request can be made by the investigators, healthcare professionals who are not members of the trial staff, or authorised LEO personnel.

Provisions are in place for 24-hour emergency unblinding of individual subject treatment. If emergency unblinding is required, the investigator can unblind a subject's treatment in the IRT. For a requester who is not a member of the trial staff and who does not have access to the

IRT (e.g., a physician at an emergency room), a local contact number for the emergency unblinding contract research organisation (CRO) is provided on the subject card (see [Appendix 3B](#)) to be used if the investigator or delegated site staff cannot be reached. The requester will provide the trial ID and subject ID to the emergency unblinding CRO who will immediately reveal the subject's treatment allocation.

The emergency unblinding CRO will clarify that the requester requires immediate unblinding without further medical consultation. Should the requester wish to discuss whether unblinding is necessary, the emergency unblinding CRO will provide the requester with the LEO 24/7 contact which will be diverted to the medical cover.

9.4 Background treatment (emollients)

The subjects should not change their usual skin care routine regarding use of emollients. However, the emollient must not be used within 2 hours before and after application of the IMP. Use of concomitant treatment is further described in Section [9.6](#).

9.5 Rescue treatment

If medically necessary (i.e., to control intolerable chronic hand eczema symptoms), rescue treatment for chronic hand eczema may be provided to the subjects at the discretion of the investigator. The investigators should make every attempt to conduct efficacy and safety assessments (for example disease severity scores, safety labs) immediately before administering any rescue treatment.

If rescue treatment is initiated, the subject must stop treatment with IMP immediately and must not re-start treatment with IMP. It must be stated in the eCRF that the subject receives rescue medication. For the purpose of the primary efficacy analyses, subjects receiving rescue treatment during the IMP treatment period will be considered as non-responders.

9.6 Concomitant medication and concurrent procedures

Any medication or vaccine that the subject receives from 6 months prior to baseline (if relevant) through follow-up period must be recorded in the subject's medical record and the eCRF along with details such as:

- Medication name.
- Indication.

- Start and stop date of administration (it will also be recorded if the medication is ongoing).
- Dosage information, including dose, unit, and frequency.
- Route of administration.
- For topical treatment, the body location must be recorded; it must also be recorded if the treatment is within 5 cm (approximately 2 inches) of the treatment area.

Similarly, any concurrent procedure must also be recorded in the subject's medical record and the eCRF. The following details will be recorded:

- Procedure.
- Body location.
- Diagnosis.
- Start and stop date (it will also be recorded if the procedure is ongoing).
- For topical treatments, it must also be recorded if the procedure is inside the treatment area.

Investigators may prescribe concomitant medications or treatments to provide adequate supportive care as deemed necessary, except for medications listed in Section 9.7. Use of emollients is described in Section 9.4.

As a rule, the subjects should not change their usual skin care routine if possible. The subjects will be asked to wear vinyl gloves when applying any other skin treatments/products to other areas of the body for other skin conditions during the trial. Normal bathing and washing is allowed with the exceptions mentioned in the instructions for use. Use of cosmetic body care products (e.g., body lotion, shampoo, bath oil), which are routinely used by the subjects, is allowed as per instructions for use, but the products should not be changed during the trial.

Excessive sunlight and sunlamps should be avoided. Sunscreen products on the body and protective gloves on the hands are recommended when exposure cannot be avoided.

9.7 Prohibited medication and procedures

The medications listed in [Panel 5](#) are prohibited during the trial. In case any prohibited treatments are used during the trial, they must be recorded as concomitant medication.

Panel 5: Prohibited medication

Medication	Prohibited from	Prohibited to
Systemic treatment with immunosuppressive drugs (e.g., methotrexate, cyclosporine, azathioprine), immunomodulating drugs (e.g., janus kinase inhibitors), retinoids (e.g., alitretinoin), or corticosteroids (inhaled or intranasal steroids corresponding to up to 1 mg prednisone for asthma or rhinitis may be used).	4 weeks prior to baseline.	End of trial.
Phototherapy e.g., PUVA or UVB therapy.	4 weeks prior to baseline.	End of trial.
Live attenuated vaccines.	4 weeks prior to baseline.	End of trial.
Cutaneously applied treatment with immunomodulators (e.g., PDE-4 inhibitors, pimecrolimus, tacrolimus) or topical corticosteroids on the hands.	2 weeks prior to baseline.	End of trial.
Cutaneously applied antibiotics on the hands.	2 weeks prior to baseline.	End of trial.
Change in systemic antihistamine therapy.	2 weeks prior to baseline.	End of trial.
Other cutaneously applied therapy on the hands (except for the use of subject's own emollient).	1 week prior to baseline.	End of trial.
Cutaneously applied treatments in regions other than the hands, which could interfere with clinical trial evaluations or pose a safety concern.	1 week prior to baseline.	End of trial.
Treatment with any marketed biological therapy or investigational biologic agents (including immunoglobulin, anti-IgE, and dupilumab): 
 Any cell-depleting agents including but not limited to rituximab. Other biologics. 	6 months prior to baseline or until lymphocyte count returns to normal, whichever is longer. 3 months or 5 half-lives, whichever is longer, prior to baseline.	End of trial. End of trial.
Any non-marketed drug substance (i.e., an agent which has not yet been made available for clinical use following registration).	4 weeks prior to baseline or 5 half-lives whichever is the longest.	End of trial.

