10.2 IMP discontinuation rules

10.2.1 Reasons for discontinuation of IMP

Subjects will discontinue IMP in the event of:

- An AE that, in the opinion of the investigator or sponsor's medical expert, contraindicates further dosing.

- Evidence of pregnancy.
- Initiation of rescue medication.
- Clinically important laboratory abnormalities:
 - Alanine aminotransferase and/or aspartate aminotransferase values $>3\times\text{ULN}$ with total bilirubin $>2\times\text{ULN}$ (unless elevated bilirubin is related to Gilbert Meulengracht Syndrome).
 - Confirmed aspartate aminotransferase and/or alanine aminotransferase $>5\times\text{ULN}$ (for more than 2 weeks).

It is not allowed to re-start IMP treatment after discontinuation of IMP.

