14.2 Trial analysis sets

All screened subjects will be accounted for in the CTR.

All randomised subjects will be included in the full analysis set and will be analysed for efficacy parameters up to Week 16. Exclusions from the full analysis set can be considered in special cases as described in ICH E9, Section 5.2.1., Full Analysis Set. If it is decided to exclude a randomised subject from the full analysis set, a justification addressing ICH E9 will be given.

A per protocol analysis set will be defined by excluding subjects from the full analysis set who fulfil any of the following criteria:

- Did not receive treatment with the IMP.
- Did not provide IGA or HECSI data following start of treatment.
- Are known to have taken the wrong IMP throughout the treatment period of the trial.
- Did not fulfil the disease defining inclusion criteria (that is, inclusion criteria 3, 4, and 5).
- Did not apply IMP at least 80% of the time in the period from date of first application of IMP to date of last application of IMP.

A safety analysis set will be defined by excluding subjects from the full analysis set who receive no treatment with IMP.

Based on the above rules, the decisions regarding inclusion/exclusion of subjects and/or subject data from the trial analysis sets will be documented in the analysis set definition document before breaking the randomisation code.

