14.3.5 Analysis of primary efficacy endpoint

The primary endpoint IGA TS at Week 16 will be analysed for the full analysis set and for the per protocol analysis set. The per protocol analysis is regarded as supportive.

IGA TS refers to IGA score of 0 (clear) or 1 (almost clear) with ≥ 2 -step improvement from baseline.

For the analysis of the primary endpoint, subjects who initiate rescue medication before Week 16 or withdraw from the trial and have no retrieved data at Week 16, will all be considered non-responders.

The Multiple Comparison Procedure – Modelling (MCP-Mod) approach (see e.g., EMA Qualification Opinion of MCP-Mod [23] or Bretz et al [24] for further details of the framework) will be used to guide dose selection. The dose-response relationship for the binary endpoint IGA TS will be modelled by the following 3 identified candidate models. These candidate models are selected based on the expected dose-response.

Linear in log: $E_0 + \delta \times \log(d + c)$,

E_{max} : $E_0 + E_{max} \times d / (ED_{50} + d)$,

Sigmoid E_{max} : $E_0 + E_{max} \times d^h / (ED_{50}^h + d^h)$,

where d is the dose (incl. vehicle), E_0 is the efficacy offset (anticipated vehicle effect), E_{max} is the asymptotic maximum effect, ED_{50} is the half-life value of E_{max} , h is the steepness at ED_{50} , δ is the slope parameter, and c is a fixed offset parameter.

The models will be adjusted for the stratification variables region and baseline IGA. The model parameters (ED_{50} , h) will be prespecified a priori by suitable guesses based on data from Japan Tobacco's dose-ranging trial QBA2-1 (25). Akaike's Information Criteria will be

used as the goodness-of-fit criterion that will drive the selection of the dose-response model that fits data best while controlling the family-wise error rate at 5%. Based on the selected model, the dose-response relationship will be estimated and presented with 2-sided 95% CI. If none of the candidate models converge, other possibilities of models and goodness-of-fit criteria will be explored. The dose-response modelling will be performed on both the total population and subjects having a baseline IGA of 3 or 4, in order to further explore heterogeneity in the disease population.

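### The per protocol set keeps subjects who used a prohibited therapy active on hand eczema, so the supportive analyses can credit that drug's effect to the randomised arm

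*Combined protocol and SAP*

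**What the plan says.** Panel 5 in Section 9.7 lists therapies prohibited until end of trial. Several act on hand eczema: topical corticosteroids and immunomodulators on the hands, phototherapy, systemic immunosuppressants, immunomodulators, retinoids and corticosteroids, and biologics. If one is used, "In case any prohibited treatments are used during the trial, they must be recorded as concomitant medication". No analysis step follows.

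Section 14.2 reads: "A per protocol analysis set will be defined by excluding subjects from the full analysis set who fulfil any of the following criteria". Five criteria are listed:

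1. received no IMP;
2. gave no IGA or HECSI data after starting treatment;
3. took the wrong IMP for the whole treatment period;
4. failed inclusion criterion 3, 4 or 5;
5. applied IMP less than 80% of the time.

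The section then ties decisions to that list: "Based on the above rules, the decisions regarding inclusion/exclusion of subjects and/or subject data from the trial analysis sets will be documented" before the code is broken.

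Rescue is handled separately. In Section 9.5, "rescue treatment for chronic hand eczema may be provided to the subjects at the discretion of the investigator", and it must be stated in the eCRF. "Initiation of rescue medication" is a reason to stop IMP (Section 10.2.1). For the primary endpoint, "subjects who initiate rescue medication before Week 16 or withdraw from the trial and have no retrieved data at Week 16" are non-responders (Section 14.3.5). Section 14.3.6 excludes HECSI data after rescue and censors time to treatment success at rescue.

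Sections 14.3.5 and 14.3.6 call for a supportive per protocol analysis of the primary and both secondary endpoints.

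**The concern.** A per protocol analysis is meant to show the effect in subjects treated as the protocol intended. Using a banned drug that works on the same disease departs from that intention more directly than missing some cream, yet only the second is an exclusion.

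Such use is foreseeable. Section 9.7 provides for recording it, and Section 5.1 describes topical corticosteroids as the commonest treatment for the disease and as effective. A subject who self-applies a leftover corticosteroid, keeps using IMP, is not flagged as rescued and is clear at Week 16 passes all five criteria and counts as a per protocol success. A reader who turns to this analysis to check the primary result for protocol departures would not learn that this departure is still in it.

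**Working it through.** **1. The five exclusions against one subject.** Take a subject who meets the inclusion criteria, applies the assigned cream at least 80% of the time, attends visits, and uses a topical corticosteroid on the hands from Week 10 without a rescue flag.

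| Criterion in Section 14.2 | Removes this subject? |
|---|---|
| No IMP received | No |
| No IGA or HECSI data on treatment | No |
| Wrong IMP throughout | No; it concerns IMP, not other drugs |
| Failed inclusion criterion 3, 4 or 5 | No; these are entry criteria |
| Under 80% IMP application | No; it measures IMP use only |

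The subject stays in. If the use had been flagged as rescue, the subject would also stay in, but as a non-responder, which does little harm to that endpoint.

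**2. The data needed for an exclusion already exist.** Section 9.6 collects drug name, indication, dates, dose, route and body location. For topical treatment, "it must also be recorded if the treatment is within 5 cm (approximately 2 inches) of the treatment area".

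**3. The plan's own figure.** Section 14.1 assumes 45% against 15% with 50 per arm at the 5% level. With pooled variance under the null, power = Φ[(Δ − 1.96·√(2·p̄(1 − p̄)/n)) / √(p₁(1 − p₁)/n + p₂(1 − p₂)/n)]. Here p̄ = 0.30, so (0.300 − 1.96 × 0.0917) / 0.0866 = 1.39 and power is 91.8%. This agrees with the stated value of slightly above 90%.

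**4. What use could do to the observed rates.** The documents give no rate of use, so all inputs here are assumptions. Let u be the share of an arm using such a drug and r the share of would-be non-responding users whom it converts. Counted as observed, p′ = p + u·r·(1 − p). If every user is instead called a non-responder, and use is unrelated to the underlying response, p′ = p·(1 − u). Differences are in percentage points; the three values are for r = 10%, 25% and 50%.

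| Use, vehicle / active | As observed: difference | As observed: power | Non-responder: difference | Non-responder: power |
|---|---|---|---|---|
| 10% / 5% | 29.4 / 28.6 / 27.1 | 90.4 / 88.0 / 83.4% | 29.25 | 91.4% |
| 10% / 10% | 29.7 / 29.25 / 28.5 | 90.8 / 89.3 / 86.7% | 27.0 | 87.2% |
| 5% / 10% | 30.1 / 30.3 / 30.6 | about 91.7% throughout | 26.25 | 84.8% |

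Example, 10% / 10% at r = 50%: active 0.45 + 0.10 × 0.50 × 0.55 = 0.4775; vehicle 0.15 + 0.10 × 0.50 × 0.85 = 0.1925; difference 28.5 points.

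Use concentrated on vehicle pulls the difference down, and use concentrated on active pushes it up slightly. Forcing non-response helps in the first row and hurts in the third, so it is not a clear improvement for the primary analysis.

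**5. What the exclusion does.** If use is unrelated to the underlying response, dropping users returns 45% and 15%. If instead every user would have failed anyway, dropping them gives p/(1 − u). At 10% in both arms that is 0.45/0.90 = 50.0% and 0.15/0.90 = 16.7%, a difference of 33.3 points. In that second case, counting them as non-responders in the full set returns 45% and 15%. The two analyses cover each other's weak case, which is why the fix has both.

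**The case against.** The strongest reply is that the plan has safeguards and that the detail belongs in the SAP. "Investigators may prescribe concomitant medications or treatments to provide adequate supportive care as deemed necessary, except for medications listed in Section 9.7", so investigators may not give Panel 5 drugs as supportive care. Section 5.5 tells subjects to contact the investigator if their eczema worsens significantly, and Section 13.6.6 makes clinically significant worsening a reportable event. Appendix 3D has the sponsor assess deviations and describe major ones in the report. Section 14.3.12 plans a blinded review, with the SAP finalised before unblinding. The text reviewed holds no separate SAP, and one might add the exclusion. Many subjects were also enrolled because topical corticosteroids had not worked for them, and Section 5.1 says pimecrolimus lacks effect, so conversion may be low. The per protocol analysis is only supportive, in a phase 2b trial with nominal p-values.

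Most of this stands and limits the weight of the point. It does not answer it: these measures reduce or report such use, but none removes the subject from a set whose membership Section 14.2 ties to its own list.

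A reader might go further and infer that the primary endpoint is unprotected, or that power and dose selection are compromised. The documents do not support that. Section 9.5 describes rescue and requires it to be stated in the eCRF. Identifying further rescue from medication records is ordinary SAP detail. Analysing other use as observed is a defensible treatment-policy choice, in keeping with a primary analysis that already provides for Week 16 data retrieved after IMP is stopped.

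**Conclusion.** The point holds for the per protocol set. As Section 14.2 is written, use of a prohibited therapy active on hand eczema does not remove a subject from the supportive analyses of the three main efficacy endpoints. This follows from the text and needs no assumption, except that no SAP outside the reviewed text adds an exclusion.

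Its numerical size cannot be established. Under the assumed use and conversion rates, the planned 30-point difference would move by between −2.9 and +0.6 points. No effect on power is claimed: the pairwise figures above show only that it could go either way. No effect on MCP-Mod was calculated or is claimed. The case for the change is that a per protocol analysis should not credit another drug's response to the assigned arm. It is a modest gap in a supportive analysis, worth closing because closing it is cheap.

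**What to change.** Add a sixth exclusion to Section 14.2: use, between first IMP application and the Week 16 assessment, of a Panel 5 therapy active on hand eczema that blinded review before code break judges able to affect the Week 16 assessment. Name the classes: topical corticosteroid or immunomodulator on the hands; phototherapy; systemic immunosuppressant, immunomodulator, retinoid or corticosteroid; biologic. Write down the dose, duration and timing that count before the review starts, so that an isolated early application does not exclude anyone. Say also whether the criterion reaches use already flagged as rescue; those subjects are already non-responders, and leaving them in avoids removing known failures.

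Keep the primary analysis on the full analysis set as planned. Add one sensitivity analysis counting the same users as non-responders for IGA treatment success.

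The cost is a slightly smaller per protocol set (at an assumed 5% to 10% use, 0.05 × 50 = 2.5 to 0.10 × 50 = 5 subjects per arm), one extra analysis and a blinded medication listing review. No new data and no change to patient care are needed. Section 14.3.12 allows the change to be made in an amendment or in the SAP.
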